### 3.15.4 Electrocardiograms

Screening ECG data will be provided in data listings.

### 3.15.5 Pulse Oximetry

Pulse oximetry measurements should only be performed in subjects with asthma or COPD. Pulse oximetry measurements, oxygen level (%), will be summarized by visit and treatment.

### 3.15.6 Physical Examinations

Physical examination data will be provided in data listings.

## 3.16 Pharmacokinetic Analyses

During the study, PK samples will be collected on Day 1 (postdose; at least 1 hour after dosing or right before the subject leaves the site, whichever is later), Day 3 (at the same approximate time as that of the nasopharyngeal swab collection, predose or postdose), and Day 5 (predose).

At the EOS Visit, a PK sample is only required for subjects who discontinue the study before the last dose of study drug is taken. The PK sample should be collected at the same approximate time as that of the nasopharyngeal swab collection.

Actual date and time of PK sample collection will be recorded in the eCRF. In addition, the site should record the date and time of last dose taken prior to the PK sample collection in the eCRF.

### 3.16.1 Analysis of PK samples

For subjects in the PK population, the concentration data for EDP-938 and each metabolite will be summarized by visit, and nominal time. For predose samples, nominal time will be set to 0. For postdose samples, nominal time will be assigned based on the closest postdose integer hour. Concentrations that are below the limit of quantitation (BLQ) will be treated as zero for the computation of descriptive statistics. If more than 50% of subjects have concentration values below BLQ, descriptive statistics will not be presented except for maximum and BLQ will be displayed for mean and minimum. The number of observations, arithmetic mean, standard deviation (SD), % coefficient of variation (%CV), median, minimum, maximum, geometric mean, and %CV of the geometric mean (%GCV) will be displayed.

Individual data will be presented in listing.

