5.7 Study Drug Dose and Administration

Complete instructions for dispensing and administering study drug are presented in the study-specific Pharmacy Manual.

Following randomization on Day 1, subjects will receive the first dose of 800 mg EDP-938 or placebo orally while at the study site. After the first dose, subjects will be instructed to take the study drug once daily on each of the 4 subsequent days. Subjects will be instructed to take the study drug orally at approximately the same time every day (± 1 hour). From Day 1, subjects will electronically record the time and date that each dose is taken.

On Day 3 and Day 5, subjects should bring their study drug with them as part of their study site visit [REDACTED] for drug accountability and for dosing of study drug on Day 5 as described below. If the subject is unable to attend the Day 3 and/or Day 5 study site visit, a home visit by a study nurse may be arranged, if feasible; refer to the Study Procedures Manual (SPM) for details.

On Day 5, the study site visit should be scheduled close to the time that the subject normally takes the study drug so that dosing can occur at the site. If the Day 5 study site visit occurs up to 4 hours after the time scheduled for dosing of study drug, then the subject should take the study drug at the site during the visit (refer to the SoA [Appendix 1]). If the Day 5 study site visit occurs more than 4 hours after the time scheduled for dosing of study drug, then the subject should take the study drug at the scheduled time.

If a subject forgets to take their study drug at the scheduled time, the dose should be taken as soon as the subject remembers; however, the following rules apply:

- No more than 1 dose should be taken on any calendar day and
- There must be a minimum of 16 hours between doses.

Note: Site staff will record the time and date of all study drug doses taken at the site.

Stopping rules for study drug administration are provided in Section 10.1.

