7.1.2 Treatment Period (Days 1 to 5)

Study Site Visits (Days 1, 3, and 5):

Subjects who meet all inclusion criteria and none of the exclusion criteria to the satisfaction of the Investigator will be eligible to enter the study and will be randomized 1:1 to receive 800 mg of EDP-938 or placebo. Subject randomization will be stratified by the presence or absence of asthma/COPD.

Eligible subjects must complete the Day 1 biological sample collections (ie, blood, urine, and nasopharyngeal swab[s]) prior to receiving the first dose of EDP-938 or placebo. Day 1 blood

and urine samples will be sent to both local (expedited testing and reporting) and central laboratories. Nasopharyngeal swab(s) will be sent to the central laboratory only.

Eligible subjects will receive an electronic data capture handheld device (ERT[®] electronic clinical outcome assessment [eCOA] Handheld eDiary) to use for the duration of the study.

[REDACTED]

The device will also serve to alert the subject when it is time for study drug dosing. The subject will receive instruction on the proper use and care of the device, including the recording of the first dose, and the device should be brought to each study site visit. In case the subject is unable to complete any assessments or recordings into the device for technical reasons, the subject will also be provided with a paper diary(ies) as a back-up.

The subject will be instructed on the use of concomitant medications during the study, including the use of acetaminophen as the study-specific analgesic/antipyretic (see [Section 5.8](#) and [Section 5.9](#)).

Subjects will receive the first dose of study drug while at the study site. After the first dose, subjects will be instructed to take 800 mg of EDP-938 or placebo once daily at approximately the same time every day (± 1 hour) on each of the 4 subsequent days. The subject will also receive instruction on the appropriate storage and transport of study drug (see [Section 5.3](#)).

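### SAP 3.16.1 puts every predose PK sample at nominal time 0, so the Day 3 row at time 0 can mix mid-interval and trough concentrations (minor)

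*SAP*

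**What the plan says.** SAP 3.16.1 says that concentrations of EDP-938 and its metabolites "will be summarized by visit, and nominal time". Two labelling rules follow. For samples before a dose: "For predose samples, nominal time will be set to 0". For samples after a dose: "For postdose samples, nominal time will be assigned based on the closest postdose integer hour". The visible text gives no acceptance window and no summary by time since the previous dose.

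The sampling rules differ by day:

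- **Day 3.** SAP 3.16 takes the sample "at the same approximate time as that of the nasopharyngeal swab collection, predose or postdose". Protocol 8.6 also links it to the swab. Neither document ties the Day 3 visit to the dosing hour.
- **Day 5.** The sample is meant to be predose. Protocol 5.7 asks for the visit to be close to the usual dosing time and has an on-site dosing rule that begins: "If the Day 5 study site visit occurs up to 4 hours after the time scheduled for dosing of study drug". If the visit is later than that, the dose is taken at its scheduled time, and the sample becomes postdose.

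The dosing hour is set on Day 1. Protocol 7.1.2 states: "Subjects will receive the first dose of study drug while at the study site". Later doses are taken at about the same time each day, within 1 hour.

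The times needed to do better are collected. Sample times go into the eCRF, and SAP 3.16 adds that "the site should record the date and time of last dose taken prior to the PK sample collection in the eCRF".

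**The concern.** Labelling a predose sample as time 0 is informative when the draw comes just before a dose at the end of a full interval. On Day 3 nothing ensures this. The Day 1 dose follows same-day consent, viral testing, ECG and randomisation, so it may fall late in the day, and that hour then carries forward. A subject who doses at 17:00 and attends at 09:00 on Day 3 gives a predose sample 16 h after the last dose. One who attends just before dosing gives a sample at about 24 h. Both are labelled 0.

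Plasma concentrations on Days 1, 3 and 5 are a named secondary endpoint (SAP 2.2.2). They come from about 35 active-arm subjects with one scheduled sample on each of these days. Protocol 4.2.2 describes Phase 2a exposure as troughs 22 to 42 times the in vitro EC90, so a reader of the report may well compare the Day 3 mean at time 0 with those multiples. If the row spans much of the dosing interval, that comparison is not valid, and the CV shown is not between-subject variability alone.

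**Working it through.** The plan gives no figure of its own to reproduce. The check derives the range of times since last dose that can share each row at time 0, then converts it to a concentration ratio.

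**Inputs from the documents**

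- Dosing interval 24 h, tolerance ±1 h (Protocol 5.7).
- Day 5 predose sample with the visit up to 4 h after the scheduled dose (Protocol 5.7, 8.6).
- At least 16 h between doses (Protocol 5.7).
- End-of-treatment visit on Day 5 with a window of +1 day (Schedule of Assessments).
- Summary cells defined by visit and nominal time (SAP 3.16.1).

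**Inputs assumed**

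- Site hours: 08:00–18:00, with 08:00–16:00 and 07:00–20:00 as alternatives.
- Half-life of 8, 12, 18 or 24 h; the legible text gives none.
- Mono-exponential decline between the two times compared.

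**Day 3, row at time 0.** For a visit at clock time V before a usual dosing time D:

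time since last dose = 24 − (D − V), ±1 h for the previous dose.

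The largest D − V is the length of the site day.

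- 08:00–18:00: 24 − 10 = 14 h up to 24 h; with ±1 h, 13 to 25 h.
- 08:00–16:00: 24 − 8 = 16 h up to 24 h; with ±1 h, 15 to 25 h.
- 07:00–20:00: 24 − 13 = 11 h up to 24 h; with ±1 h, 10 to 25 h.

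**Day 5, row at time 0.** With the visit between 0 and 4 h after the scheduled time, the range is 24 − 1 = 23 h to 24 + 4 + 1 = 29 h. If the Day 4 dose was taken late, the 16 h minimum gap still sets a floor for a sample drawn at the Day 5 dose, so the widest range is 16 to 29 h.

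**Concentration ratio** across a range of Δ hours = 2^(Δ / half-life).

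| Row at time 0 | Δ (h) | 8 h | 12 h | 18 h | 24 h |
|---|---|---|---|---|---|
| Day 3, 13–25 h | 12 | 2.8 | 2.0 | 1.6 | 1.4 |
| Day 5, 23–29 h | 6 | 1.7 | 1.4 | 1.3 | 1.2 |
| Day 5 after a late Day 4 dose, 16–29 h | 13 | 3.1 | 2.1 | 1.7 | 1.5 |

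For example, the Day 3 ratio at a 12 h half-life is 2^(12/12) = 2.0.

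**Day 5/EOT labelling.** This step needs no half-life. A Day 5 sample drawn just before an on-schedule dose is about 24 h after the Day 4 dose and is labelled 0. If the visit falls on Day 6, the Day 5 dose has been taken at its scheduled time. A sample drawn at the usual dosing hour is then also about 24 h after the last dose, but it counts as postdose and is labelled 24 h. The same time since dose therefore lands in two cells of one visit.

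**The case against.** The strongest case on the other side has several parts.

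*The contrast could be overstated.* A reader might infer that a 16 h sample from Day 3 and a 28 h sample from Day 5 fall into one row. They do not: the summaries are by visit, so the two days stay apart. This stands, and each day must be sized on its own.

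*Day 5 is largely protected.* A reader might also infer that Day 5 mixes mid-interval samples. The scheduling rule, the 4 h limit and the 16 h minimum gap keep Day 5 predose samples at trough or late trough when dosing is on schedule. This stands too.

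*The Day 6 label could be read as an error.* A sample 24 h after the final dose labelled 24 h postdose is accurate in itself. What remains is the inconsistency with samples at the same time since dose that are labelled 0.

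*The SAP does not call these values troughs.* True. The trough language in Protocol 4.2.2 describes Phase 2a results and defines no endpoint here. The risk lies in how the row will be read.

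*Nothing is lost.* Actual times are recorded and individual data are listed, so time since dose can be recovered. Time 0 for predose samples is a usual convention, and the PK analysis is descriptive. All of this limits the severity, but a listing does not correct the summary table.

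*Other analyses may exist.* Some PK text in Protocol 8.6 is redacted, as is a block after SAP 3.17, so analyses using actual times may be planned there. That cannot be excluded. The point is confined to the summary that SAP 3.16.1 specifies.

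**Conclusion.** The point holds, mainly for Day 3, and is minor. The Day 3 row at time 0 can cover about 13 to 25 h since the last dose, a concentration ratio of about 2.8 to 1.4 over half-lives of 8 to 24 h. Its mean should not be read as a trough, nor its CV as between-subject variability alone. For Day 5 the range is about 23 to 29 h and the ratio about 1.7 to 1.2. The Day 5/EOT visit also has the labelling inconsistency at about 24 h.

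The Day 3 range depends on the assumed site hours: 15 to 25 h for 08:00–16:00 and 10 to 25 h for 07:00–20:00. The ratios depend on the assumed half-lives and on mono-exponential decline. These are possible ranges; the documents do not say how many subjects would fall towards the early end. Missed doses would widen them. No test, sample size or efficacy conclusion depends on these rows.

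**What to change.** In SAP 3.16.1:

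1. Derive actual time since last dose for every PK sample from the sample and last-dose times already in the eCRF.
2. Summarise Day 3 and Day 5 concentrations by time since last dose.
3. Prespecify a window around 24 h for any value described as trough, and apply it alike to samples drawn before the Day 5 dose and to samples from a Day 6 visit. The documents give no basis for a particular width, so the sponsor should choose and justify it.
4. Plot all concentrations against time since last dose. Protocol 11.8 already allows for concentration-time figures and leaves details to the SAP.

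The cost is one SAP paragraph and minor programming, with no new data. The drawback is fewer subjects per summary cell, from an active arm of about 35.

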### 3.17 Subgroup and Covariate Analyses

TSS AUC from Day 1 through Day 14 and RSV RNA viral load AUC from Day 1 through Day 14 will be analyzed by RSV type (A or B) using the same ANCOVA analysis as described in Section 3.14.1 and Section 3.14.2, except that RSV type and treatment by RSV type interaction are added to the model.

Other subgroup analyses may be explored as allowed by data.

[REDACTED]

### 3.19 Interim Analyses

No interim analysis will be performed in this study.

### 3.20 Multiplicity

No adjustment will be made for multiple comparisons.

### 3.21 Treatment by center interaction analysis

No analysis will be made to assess the treatment-by-center interaction.

## 5. APPENDICES

### 5.1 Schedule of Assessments

Period Day	Screening	Treatment					Follow-up			
	1 Screening	1 Eligible Subjects a	2	3	4	5 (+1 d) EOT	6-8	9 (±1 d)	10-13	14 (±1 d) EOS b
Study site visit	X			X c		X c		X c		X c
Informed consent form d	X									
RSV/influenza rapid diagnostic test e	X									
Inclusion/Exclusion criteria	X									
SARS-CoV-2 rapid diagnostic test f										
Demographics	X									
Medical history	X									
Smoking history	X									
Prior medications	X									
Vital sign measurements g	X					X				X
12-Lead ECG (resting)	X									
Physical examination h	X									
Weight, height, and BMI i	X									X
Pulse oximetry j	X					X				X
Frailty scale score (see SPM)	X									
Pregnancy test k	X (urine)	X (serum)								X (urine)
FSH l		X								
Clinical laboratory tests ma		X				X				X
Randomization n		X								
eCOA Handheld eDiary o		X								X
RSV symptom diary eCOA p		X	X	X	X	X	X	X	X	X
████████████████████		X	X	X	X	X	X	X	X	X
NP swab collection: confirmatory respiratory pathogen panel		X								
NP swab collection: RSV RNA quantitation of viral load		X		X		X		X		X
████████████████████		X		X		X		X		X
RSV serology collection		X								X
████████████████████		X								X
Study drug dosing s		X s	X	X	X	X s				
Study drug accountability t				X		X				
PK sample collection		X u		X u		X u				X v
Concomitant medications w		X	X	X	X	X	X	X	X	X

Adverse events	X	X	X	X	X	X	X	X	X	X
----------------	---	---	---	---	---	---	---	---	---	---

Abbreviations: BMI = body mass index; COPD = chronic obstructive pulmonary disease; d = day; ECG = electrocardiogram; eCOA = electronic clinical outcome assessment; EOS = end-of-study; EOT = end-of-treatment; FLU-PRO = InFLUenza Patient-Reported Outcome; FSH – follicle-stimulating hormone; ICF – informed consent form; NP – nasopharyngeal; PK – pharmacokinetic; RSV – respiratory syncytial virus; SARS-COV-2 = severe acute respiratory syndrome coronavirus 2; SPM = Study Procedures Manual.

Note: Refer to the Laboratory Manual for sample collection and processing details.

- a Day 1 assessments to be performed in randomized subjects.
- b Subjects who discontinue treatment early (ie, prior to completing 5 days of dosing) or the study early (ie, prior to Day 14) should return to the study site within 24 hours and no more than 48 hours later to complete the EOS procedures.
- c Visit assessments may be completed at the study site or by a study nurse via a home visit, if feasible; refer to the SPM for details. It is anticipated that every reasonable effort will be made to ensure that subjects return to the site for the Day 3 and Day 5 visits.
- d Informed consent must be obtained prior to conducting any study-specific assessments. For this study, there will be two ICFs. Subjects will review and sign the Rapid Viral Screen ICF prior to RSV and influenza screening. Subjects whose swab sample tests positive for RSV and negative for influenza virus may proceed for further screening. Such subjects will be required to sign the full study ICF prior to performing any further study-specific assessments. After signing the full study ICF, subjects will undergo further screening procedures to determine study eligibility.
- e A nasal (or NP) swab sample will be collected to obtain respiratory secretions for a rapid diagnostic screen for RSV and influenza A/B.
- f Subjects who sign the full study ICF and whose swab sample test results are positive for RSV and negative for influenza will be screened for SARS-CoV-2, using a rapid diagnostic test.
- g Vital signs include heart rate, respiratory rate, systolic and diastolic blood pressure, and body temperature. Vital signs will be measured after the subject has been supine for a minimum of 5 minutes.
- h A full physical examination will be performed at Screening. Any subsequent physical examinations performed at the discretion of the Investigator will be targeted to new signs and symptoms including specific assessments of any changes from previous status.
- i Height will be documented at Screening only. Body mass index will be calculated at Screening (to assess eligibility) according to the following equation:  $BMI = \text{weight (kg)}/\text{height (m)}^2$ .
- j Pulse oximetry measurements should only be performed in subjects with asthma or COPD.
- k Pregnancy testing will be performed in female subjects of childbearing potential. A urine pregnancy test will be performed at Screening and at the EOS Visit. In addition, on Day 1, blood will be collected for a serum pregnancy test to be performed by the central laboratory. The screening urine pregnancy test results will be used to qualify subjects at study entry. Refer to Protocol Section Error! Reference source not found. for pregnancy testing requirements for postmenopausal females.
- l Follicle-stimulating hormone should be tested in postmenopausal females. Refer to Protocol Section Error! Reference source not found..
- m Clinical laboratory tests include chemistry, hematology, and urinalysis. See Protocol Section Error! Reference source not found. and Error! Reference source not found. for details regarding Day 1 sample collection and evaluations for the local and central laboratory(ies).
- n Subjects who meet all inclusion criteria and none of the exclusion criteria to the satisfaction of the Investigator, including the screening ECG and the screening urine pregnancy test, will be eligible to enter the study and will be randomized 1:1 to receive 800 mg of EDP-938 or placebo. Subject randomization will be stratified by the presence or absence of asthma/COPD.
- o Eligible subjects will receive an electronic data capture handheld device (ERT® eCOA Handheld eDiary) on Day 1 and will return the device to the study site at the EOS Visit. Refer to Protocol Section Error! Reference source not found. for additional details.
- p The RSV symptom diary will be self-completed by subjects twice daily at the same times each day  $\pm 2$  hours as an eCOA. If a subject plans to take acetaminophen within 2 hours of the scheduled RSV symptom diary completion, then the RSV symptom diary should be completed immediately before the subject takes acetaminophen or 4 hours after taking acetaminophen.

[REDACTED]

[REDACTED]

[REDACTED]

[REDACTED]

- s Study drug (EDP-938 or placebo) should be administered at the study site on Days 1 and 5. On Day 5, the study site visit should be scheduled close to the time that the subject normally takes the study drug so that dosing can occur at the site. From Day 1, subjects will electronically record the time and date that each dose is taken. See Protocol Section Error! Reference source not found. for additional dosing details.
- t Study drug accountability by tablet count and review of the electronic dosing record completed by the subjects.

- u On Day 1, collect one postdose plasma PK sample, at least 1 hour after dosing or right before the subject leaves the site, whichever is later. On Day 3, collect one plasma PK sample at the same approximate time as that of the NP swab collection. On Day 5, collect one predose PK sample. If the subject takes the study drug prior to the study site visit, a PK sample should be taken at the same approximate time as that of the NP swab collection. See Protocol Section Error! Reference source not found. and Section Error! Reference source not found. for additional details.
- v At the EOS Visit, a PK sample is only required for subjects who discontinue the study before the last dose of study drug is taken. The PK sample should be collected at the same approximate time as that of the NP swab collection.
- w Acetaminophen use will be permitted only for the relief of fever or pain. Subjects will electronically record the date and time of any acetaminophen use. See Protocol Section Error! Reference source not found. for additional details on acetaminophen use.

## 5.2 RSV Symptom Diary

The RSV Symptom Diary includes 13 items that assess the severity of RSV-related signs and symptoms. The 13 items are as follows: Nasal discharge, Nasal congestion (stuffy nose), Malaise/tiredness, Headache, Sinus congestion (sinus pressure), Sneezing, Sore throat, Hoarseness, Cough, Shortness of Breath, Respiratory wheeze, Earache, and Symptoms of fever. For each item, severity is rated using a 4-point scale: 0=absent, 1=noticeable, 2=Bothersome but does not interfere with activities, 3=Bothersome and interferes with activities. The total symptom score (TSS) is calculated as the sum of item scores across all 13 items. If *any* of the 13 observed values are missing the total symptom score will not be calculated for that assessment. The TSS ranges from 0 to 39 with higher scores indicating more severe symptoms.

The RSV Symptom Diary will be completed by subjects using a handheld device. Each subject will also be provided with a paper diary(ies) as a back-up, in case the subject is unable to complete the RSV symptom diary assessment for technical reasons. Diaries will be completed twice daily from Day 1 (date of first dose) through Day 14 at the same times each day  $\pm$  2 hours. Subjects are instructed to rate the severity of symptoms experienced in the last 12 hours for the morning diary on Day 1 then the maximum since the last completed diary for the subsequent diaries.

Throughout the study the subject may take acetaminophen for pain and fever relief. The subject should not take other pain relievers such as ibuprofen or naproxen. Each time the subject completes the diary acetaminophen use needs to be recorded. The time of the day the subject takes acetaminophen will be important to document due to the confounding effect on the primary analysis. If a subject plans to take acetaminophen within 2 hours of a scheduled RSV symptom diary completion, then the RSV symptom diary should be completed immediately before the subject takes acetaminophen or 4 hours after taking acetaminophen.

[REDACTED]

[REDACTED]

[REDACTED]

[REDACTED]

[figure not shown]
[REDACTED]

[REDACTED]

[REDACTED]

[REDACTED]

[REDACTED]

[Redacted text block]

[Redacted text block]

